The first dose of NGM282 (Day 1) and doses at Weeks 2, 4, 6, 8, 12, 18, and 24 study visits will be self-administered in the clinic, with all other doses throughout the treatment period self-administered at home. Self-administration of NGM282 or placebo should occur as close as possible to the same time each day for every dose. Subjects will return to the clinic on Weeks 2, 4, 6, 8, 12, 18 and 24 for on-treatment assessments and to be dispensed NGM282 or placebo study-drug kits through Week 18. LDL-C (LDL-direct may be used if LDL-C was not able to be analyzed) will be evaluated at Weeks 2, 4, 8, and 12 in all subjects for possible increases in lipid levels associated with NGM282 or placebo administration. Rosuvastatin will be started in subjects meeting specific LDL-C level criteria. The specific dosing and administration of rosuvastatin will be based on whether the subject is statin naïve versus statin experienced and LDL-C levels at Weeks 2, 4, and 8. A decision about possible second-line lipid-lowering therapy with ezetimibe will be made on a case by case basis for subjects that have not achieved an adequate response or are unable to tolerate rosuvastatin. Bottles of rosuvastatin tablets will be dispensed to all subjects initially and instructions to initiate dosing are dependent on observed lipid levels according to the dosing algorithm in [Section 10.4](#). Week 24 will be the EOT clinic visit and subjects will return to the clinic at Week 30 (or 6 weeks after last dose) for an EOS follow-up visit. Subjects are required to undergo MRI performed during Screening and at Weeks 6, 12, 24 (EOT)/Early Withdrawal, and 30 (EOS) visits.

This cohort will have two other assessments performed to assess liver histology in addition to MRI-PDFF. [REDACTED]

[REDACTED] An additional post-treatment liver biopsy will be performed at Week 24. The purpose of this biopsy is to assess changes in liver histopathology (including changes in the NAS, resolution of NASH, and changes in fibrosis) and compare and correlate to the liver imaging studies and key serum biomarkers collected during the study.

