#### **9.6.7 Week 12 Procedures**

Subjects will report to clinic visit fasted and not dosed with NGM282. The following procedures will be performed:

Pre-dose:

- Measure body weight, BMI, and waist circumference.
- Conduct physical examination.
- Obtain 12-lead ECG (after subject has been supine for at least 5 minutes).
- Measure vital signs (including temperature, respiratory rate, and seated blood pressure and pulse).
- Obtain blood and urine for 10-hour fasted clinical laboratory samples (if not fasted, chemistries and lipid panel will need to be retested)
  - Results are blinded for ALT, AST, Total Cholesterol, LDL, HDL and triglycerides
- Obtain an MRI assessment.
- Record concomitant medications.
- Record new and/or changes to AEs.

In-clinic dosing and dispensing:

- Collect old NGM282 study-drug kit/diary and conduct reconciliation.
- Collect old rosuvastatin medication bottle/diary and conduct reconciliation.

- Dispense new NGM282 study-drug kits (5) and diary.
- Dispense new rosuvastatin medication/diary.
- Oversee subject's NGM282 study-drug self-administration (from new kit).
- Perform LISSA evaluation.

Before clinic discharge:

- Obtain 2-hour post-dose PK blood sample.
- Remind subject to bring study drug kits/diary and to not self-inject NGM282 at home on clinic visit days.
- Schedule Week 18 visit and remind subject for home dosing to administer NGM282 or placebo as close as possible to the same time each day

Lipid-Lowering Therapy Assessment:

- NGM Medical Monitor/designee will evaluate LDL-C level as outlined in [Section 10.4](#) and inform site to:
  - Continue with current therapy
  - Evaluate additional lipid-lowering therapy with ezetimibe for statin non-responder
  - For subjects taking statins, evaluate tolerability and if deemed necessary, subject may be considered for alternative second-line lipid lowering therapy with ezetimibe .
- The site will then contact the subject with further instructions

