Rosuvastatin will be started in subjects meeting specific LDL-C level criteria. The specific dosing and administration of Rosuvastatin will be based on whether the subject is statin naïve versus statin experienced and LDL-C levels at Weeks 2, 4, and 8 (LDL-direct may be used if LDL-C was not able to be analyzed). A decision about possible second-line lipid-lowering therapy with ezetimibe will be made on a case-by-case basis for subjects that have not achieved an adequate response or are unable to tolerate rosuvastatin. Bottles of Rosuvastatin tablets will be dispensed to all subjects initially and instructions to initiate dosing are dependent on observed lipid levels according to the dosing algorithm in (Appendix A). Week 24 will be the EOT clinic visit and subjects will return to the clinic at Week 30 (or 6 weeks after last dose of NGM282 or placebo) for an EOS follow-up visit. Subjects are required to undergo MRI performed during Screening and at Weeks 6, 12, 24 (EOT)/Early Withdrawal, and 30 (EOS) visits.

This cohort will have two other assessments performed to assess liver histology in addition to MRI-PDFF. [REDACTED]

[REDACTED] where available at the local radiology center.

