6.2.2. Study Day

The date of first dose of study drug is designated as Day 1. Study days for screening visits are negative numbers and there will be no study day 0.

Study day will be calculated relative to first study drug administration. If the date of interest occurs on or after the first study drug administration date, study day will be

Amendment Final V 2.0

calculated as (date of interest - first study drug administration date) + 1. If the date of interest occurs prior to the first study drug administration date, study day will be calculated as (date of interest - first study drug administration date).

A subject's treatment end date is defined by the subject's last dose date in the study. A subject's study end date is defined by the date of the subject's last assessment in the study.

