9.2. ADVERSE EVENTS

AEs, including serious AEs, will be coded using the MedDRA Version 18.0. The number and percentage of subjects experiencing an AE will be summarized for each system organ class (SOC) and preferred term (PT) by treatment group. In addition, AEs will be tabulated according to severity, causality, and relation to the study drug (both NGM and Rosuvastatin).

All AE summaries will be restricted to Treatment Emergent Adverse Events (TEAEs) only. TEAEs are defined as AEs that commence on or after the date of first study drug administration. AEs without an onset date or time will be defined as treatment emergent, except if an incomplete date (e.g., month and year) clearly indicates that the event started prior to the start of first administration of study drug or if the AE stop date indicates that the event started or stopped prior to the start of first administration of study drug. Please refer to Section 6.3 for determination of TEAEs for completely or partially missing dates.

The intensity of AEs is rated by CTCAE v4.03. For both NGM282 and Rosuvastatin, adverse events might be not related, possibly related, probably related and definitely related to these study drugs.

For the summaries of AEs, subjects who experience the same AE (in terms of the MedDRA preferred term) more than once will be counted only once for that event. Separate summaries will be provided for AEs by intensity, causality, and relationship to study drug. For summaries by SOC, PT, and maximum intensity, a subject is counted once at the highest intensity level for which the event occurred at the SOC level and the highest intensity level for each unique PT within that SOC level. Therefore, subjects may only contribute once to each PT and once to each SOC level. Summaries by relatedness would be handled similar to the summaries by intensity.

The summaries presenting frequency of AE by SOC and PT will be ordered by overall descending frequency of SOC and then, within a SOC, by overall descending frequency of PT.

The following tables will be summarized for adverse events.

Amendment Final V 2.0

- An overall summary of the number and percentage of subjects reporting any TEAEs, serious TEAEs, NGM282-related TEAEs, Rosuvastatin-related TEAEs, TEAEs leading to withdrawal and TEAEs leading to death.
- TEAEs overall and by system organ class and preferred term
- TEAEs by CTCAE grade, overall and by system organ class and preferred term.

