- TEAEs of CTCAE grade 3 or higher, overall and by system organ class and preferred term.
- TEAEs leading to withdrawal, overall and by system organ class and preferred term
- Serious TEAEs, overall and by system organ class and preferred term
NGM282-related
- NGM282-related TEAEs overall and by system organ class and preferred term
- TEAEs by maximum relationship to NGM282, overall and by system organ class and preferred term
- NGM282-related TEAEs leading to withdrawal, overall and by system organ class and preferred term
- NGM282-related Serious TEAEs, overall and by system organ class and preferred term Rosuvastatin-related
- Rosuvastatin-related TEAEs overall and by system organ class and preferred term
- TEAEs by maximum relationship to Rosuvastatin, overall and by system organ class and preferred term
- Rosuvastatin-related Serious TEAEs, overall and by system organ class and preferred term
- Rosuvastatin-related TEAEs leading to withdrawal, overall and by system organ class and preferred term

For the rosuvastatin-related summary tables, only subjects who received rosuvastatin will be included. All AEs will be provided in listings regardless of TEAEs or not. All Serious AEs and AEs leading to study drug withdrawal and death will be provided in separate listings.

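### The rosuvastatin adverse event tables use the Day 1 injection as their onset date, so the maximum-relationship table counts events that began before any study rosuvastatin was taken.

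*SAP*

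**What the plan says.** SAP 9.2 treats both NGM282 and rosuvastatin as study drugs and restricts all adverse event summaries to treatment-emergent events. It gives one definition: "TEAEs are defined as AEs that commence on or after the date of first study drug administration". SAP 6.2.2 fixes the anchor: "The date of first dose of study drug is designated as Day 1". In the 24-week histology cohort that is the NGM282 or placebo injection, because Protocol 9.6.2 (Day 1) dispenses no rosuvastatin and Protocol 9.6.3 first dispenses it at Week 2.

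Four tables follow under the rosuvastatin heading of SAP 9.2. Three contain only events judged related to rosuvastatin (all, serious, and leading to withdrawal). The fourth shows all treatment-emergent events by maximum relationship to rosuvastatin, so it includes unrelated ones. For the set, "For the rosuvastatin-related summary tables, only subjects who received rosuvastatin will be included". The statistic throughout is a subject count: "The number and percentage of subjects experiencing an AE will be summarized".

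On timing, SAP 3.4 states: "Bottles of Rosuvastatin tablets will be dispensed to all subjects initially and instructions to initiate dosing are dependent on observed lipid levels". Protocol 10.4.2 ties dosing to LDL-C at Weeks 2, 4 and 8 or to the medical monitor's discretion. Adverse events are recorded through follow-up, which ends at Week 30.

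**The concern.** Rosuvastatin safety in this cohort is a stated secondary objective (SAP 3.2, Protocol section 6), and these tables are the planned adverse event summaries for it. A table of events in rosuvastatin users should not contain events that could not have followed rosuvastatin. Here it does: a user's events from the first weeks of NGM282 or placebo alone enter the table because the clock started with the injection.

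Those weeks are not neutral. Protocol 5.1.3 names gastrointestinal symptoms and injection-site reactions as the most frequent events with NGM282 in the diabetes study. Someone reading the any-event total as the experience of subjects on rosuvastatin would be reading partly the experience of starting NGM282.

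**Working it through.** The plan states no figure on this point, so there is nothing to reproduce. The check has three steps.

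**1. Share of the window before rosuvastatin.** Inputs: 24 weeks of treatment plus 6 weeks of follow-up, 30 weeks in all (SAP 3.4), and possible starts at Weeks 2, 4 and 8 (Protocol 10.4.2). Share = start week / 30.

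- Week 2: 2/30 = 6.7%
- Week 4: 4/30 = 13.3%
- Week 8: 8/30 = 26.7%

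These are slight understatements, because the site contacts the subject only after the visit's LDL-C result has been reviewed. The Week 8 figure is conditional. Protocol 10.4.2 lists Week 8 among the decision points, but for this cohort Protocol 9.6.6 (Week 8) offers only continuing or titrating, whereas 9.6.3 and 9.6.4 (Weeks 2 and 4) include starting. The passages need to be reconciled.

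**2. Direction of the effect.** The tables report the percentage of subjects with at least one event. There is no person-time denominator, so a longer window can raise a subject's chance of being counted but cannot lower it. The bias is upward.

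**3. Illustrative size in the maximum-relationship table.** Assume a constant hazard h per week for a first event of any cause. The documents give no such rate, so two values are shown. Percentage of subjects with an event = 1 − exp(−h × weeks counted). The planned rule counts 30 weeks; a rosuvastatin onset rule counts 30 minus the start week.

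| h per week | Planned rule, 30 weeks | From Week 2 (28 weeks) | From Week 4 (26 weeks) | From Week 8 (22 weeks) |
|---|---|---|---|---|
| 0.01 | 25.9% | 24.4% | 22.9% | 19.7% |
| 0.03 | 59.3% | 56.8% | 54.2% | 48.3% |

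The excess from the planned rule is 1.5 to 6.2 percentage points at the lower hazard and 2.5 to 11.0 at the higher one. If events cluster soon after the first injection, a constant hazard understates it.

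**The case against.** The strongest reply is that the clock touches little that matters. Three of the four tables hold only rosuvastatin-related events. Protocol 11.2 requires a separate relationship judgement for rosuvastatin, and its not-related category rests partly on the absence of a reasonable time sequence from dosing. An event before the first tablet should therefore land in the not-related row of one table. This stands, and it is why the point is minor. It does not remove the point, because that row and the any-event total are still printed for rosuvastatin users under a rule that does not fit them.

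A second reply is that the pre-start weeks are not statin-free for everyone. Statin-experienced subjects keep their own statin through Week 2, and Protocol 8.1.1 allows this to be rosuvastatin below 20 mg/d. This also stands: for those subjects an early event could properly be judged related to rosuvastatin, so an onset rule must say how they are counted.

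Two stronger readings are tempting. The first is that unexposed time dilutes the rosuvastatin rates. Step 2 above shows that it cannot.

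The second is that bottles go to all subjects, so the denominator is the whole cohort. On that reading, with an assumed 30 takers, 4/30 = 13.3% would print as 4/75 = 5.3%. The wording does not support it. SAP 5.2 and 5.3 use receive for a dose, while SAP 3.4 uses dispensed for bottles. Protocol 10.4.2 has only subjects meeting on-treatment criteria told to take the drug. A restriction to recipients would also exclude almost nobody if being handed a bottle counted. Under the ordinary reading the dilution is zero.

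A reader might also infer that statin intolerance inflates NGM282 withdrawals, since Protocol 9.6.7 provides that "For subjects taking statins, evaluate tolerability and if deemed necessary, subject may be considered for alternative second-line lipid lowering therapy with ezetimibe". But SAP 9.2 has separate withdrawal tables for events related to each drug, so only the all-cause table could mix them. SAP 7.1 reports discontinuation from treatment and from study. The table index is redacted and the mock-ups are a separate document, so missing titles or footnotes cannot be held against the plan.

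**Conclusion.** The point holds for one table. As written, the maximum-relationship table for rosuvastatin will include events with onset before the first study tablet, drawn from 6.7% or 13.3% of the 30-week window for a Week 2 or Week 4 start, and from 26.7% if a Week 8 start is possible. The counts go up, mainly in the not-related row and the any-event total. How far depends on event rates and start times that the documents do not give; the percentages in the table above are illustrations under an assumed constant hazard.

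The conclusion rests on reading the first study drug dose as the Day 1 injection. SAP 9.2 calls both products study drugs, so its phrase alone does not settle which is meant, but the Day 1 definition and the visit schedule do. Severity is minor: the tables are descriptive and no efficacy analysis is affected. The meanings of received and of withdrawal are matters of wording to tidy and would not justify a finding on their own.

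**What to change.** In SAP 9.2, add that the rosuvastatin tables count only adverse events with onset on or after the subject's first documented on-study rosuvastatin dose. The dates come from the administration data already planned for Listings 16.2.5.3 and 16.2.5.4. State how subjects already taking rosuvastatin at Screening are counted.

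Two clarifications belong in the same edit: that received means at least one documented rosuvastatin dose, and which drug (or the study) each leading-to-withdrawal table refers to. Separately, Protocol 9.6.6 and 10.4.2 should be reconciled on whether rosuvastatin can be started at Week 8, since this determines how long the pre-rosuvastatin period can be.

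The cost is a few sentences, one derived onset flag, and slightly lower counts in one descriptive table. No new data are needed.

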9.3. LABORATORY EVALUATIONS

Laboratory data (hematology, biochemistry, and urinalysis) will be summarized by treatment group, fibrosis stage and time point. Actual values and change from baseline will be presented for lab parameters with continuous measures. In addition, frequency tabulations of categorical urinalysis lab parameters will also be presented by treatment

Amendment Final V 2.0

group and time point. Shift tables from baseline clinical grade (low/normal/high) will also be presented for chemistry and hematology laboratory parameters.

Individual data listings of laboratory results will be presented for each subject. Laboratory values will be compared to normal ranges; out of range and clinically significant laboratory values will be identified in the listings (low, high).

Anti-drug antibodies, neutralizing antibodies and urine microscopy evaluation will be listed only.

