Samples for analysis of ADAs, NAbS, and exploratory biomarkers will be collected as outlined in the respective Schedules of Study Procedures (double-blind, [Table 2](#); open-label, [Table 3](#); placebo-controlled 24-week histology, [Table 4](#)). All NAb samples will be collected as scheduled, and analyzed only if necessary based on ADA results.

Exploratory biomarkers, ELF panel, [REDACTED] will be assessed as outlined in the respective Schedules of Study Procedures (open-label, [Table 3](#); placebo-controlled 24-week histology, [Table 4](#)).

Processing, storage, and shipping instructions for the above will be presented in a separate Lab Manual.

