5. ANALYSIS POPULATIONS

5.1. INTENT-TO-TREAT POPULATION

All randomized subjects will be included in the Intent-to-Treat (ITT) population. The ITT population will be used to summarize subject enrollment and disposition and will be based on randomized treatment if this differs from actual treatment received.

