6. GENERAL ASPECTS FOR STATISTICAL ANALYSIS

6.1. GENERAL METHODS

Unless otherwise specified, for numeric data, descriptive statistics will include the number of subjects with data to be summarized (n), mean, standard deviation (SD), median, minimum (min), and maximum (max). The same number of decimal places as used in the raw data will be presented when reporting min and max, 1 decimal place more than in the raw data will be presented when reporting mean and median, and SD. If the raw data have 3 decimals or more, 3 decimals will be presented for the mean, median, min and max, and SD.

All categorical/qualitative data will be presented using frequency counts and percentages. All percentages will be rounded to 1 decimal point, with the denominator being the number of subjects in the relevant population, unless otherwise stated. Percentages equal to 100 will be presented as 100%; percentages will not be presented for zero frequencies but the categories whose counts are zero will be displayed for the sake of completeness.

Unless otherwise specified, all the tables will be summarized by treatment group (and overall, if applicable). All the listings will be sorted by treatment group, subject number and assessment date/time.

All confidence intervals (CIs) will be two-sided and will use 95% confidence levels. Any analyses requiring significance testing will use a two-sided test at the 5% significance level, unless otherwise specified.

In general, only data from nominal scheduled visits will be presented in the summary tables and figures unless otherwise specified. Data from unscheduled visits will not be summarized but will be presented in the data listings.

All analyses and outputs will be generated using SAS® version 9.4 (or higher).

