6.2. KEY DEFINITIONS

6.2.1. Baseline

Unless otherwise specified, baseline will be defined for each subject and will be defined as the last available, valid, non-missing assessment reported on or before the start of first study drug administration.

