13. APPENDIX A

[REDACTED]

[REDACTED]

Table 2 Schedule of Study Procedures for Placebo-Controlled 24 Week Histology Cohort

Amendment Final V 2.0

Vitamin D		X					X		X	X
PK blood samples ^g		X	X	X	X	X	X	X	X	X
Anti-drug antibodies (ADAs)		X	X	X	X	X	X	X	X	X
Neutralizing antibodies (NAb)		X	X	X	X	X	X	X	X	X
ELF Panel		X			X		X		X	X
		█	█	█	█	█	█	█	█	█

ADA = anti-drug antibody; AE = adverse event; AFP = alpha fetoprotein; BMI = body mass index; C4 = 7-alpha-hydroxy-4-cholesten-3-one; CBC = complete blood count; D = Day; ECG = electrocardiogram; ELF = enhanced liver fibrosis; EOS = End of Study; EOT = End of Treatment; EW = Early Withdrawal; HIV = human immunodeficiency virus; HOMA-IR = homeostasis model assessment—estimated insulin resistance; hr. = hour; [REDACTED] INR = International Normalized Ratio; IWRS = Interactive Web Response System; LISSA = local injection-site symptom assessment; [REDACTED] MRI = magnetic resonance imaging; NAb = neutralizing antibody; PK = pharmacokinetic; UA = urinalysis; W = week.

- ^a There should be a minimum of 14 days between Screening and Day 1 visits for adequate separation of the repeated Chemistry (liver function tests) and International Normalized Ratio assessments.
- ^b Screening MRI will serve as baseline for efficacy endpoint analysis. Adiposity assessments will be collected as part of the standard MRI procedure at all sites.
- ^c [REDACTED]
- ^d All subjects are required to have a liver biopsy result at Screening and additional liver biopsy at Week 24. A Screening liver biopsy will be performed only in subjects who do not have historical biopsy available within 3 months of Screening.
- ^e Lab results for ALT, AST, Total Cholesterol, LDL, HDL and triglycerides are blinded to site from Week 2 onward.
- ^f A serum pregnancy test will be performed on all female subjects at Screening, Week 24, and Week 30. A urine pregnancy test will be performed on all female subjects at Day 1 (pre-dose).
- ^g PK blood samples will be collected in all subjects before dosing themselves in the clinic (pre-dose) and at 2 hours post-dose at Day 1, Week 12, and Week 24.
- ^h Rosuvastatin will be dispensed at Weeks 2, 4, 8, 12 and 18 visits and subjects will be provided further dosing instruction based on their LDL-C levels and whether they are statin-naïve versus statin experienced. Subjects on a statin at screening will be dispensed additional rosuvastatin at Week 24 and continue through Week 30.

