17. INDEX OF FIGURES

18. INDEX OF LISTINGS

Listing Number	Title
Listing 16.2.1.1	Listing of Subject Enrolment (Intent-to Treat)
Listing 16.2.1.2	Listing of Subject Disposition (Intent-to Treat)
Listing 16.2.2.1	Listing of Inclusion/Exclusion Criteria (Intent-to Treat)
Listing 16.2.2.2	Listing of Protocol Deviations (Intent-to Treat)
Listing 16.2.4.1	Listing of Demographic Characteristics I (Intent-to Treat)
Listing 16.2.4.2	Listing of Demographic Characteristics II (Intent-to Treat)
Listing 16.2.4.3	Listing of Liver Biopsy Histopathology (Intent-to Treat)
Listing 16.2.4.4.1	Listing of Previous Diagnoses -I (Intent-to Treat)
Listing 16.2.4.4.2	Listing of Previous Diagnoses - II (Intent-to Treat)
Listing 16.2.4.5	Listing of Medical History (Intent-to Treat)
Listing 16.2.4.6	Listing of Screening Viral Laboratory Tests (Intent-to Treat)
Listing 16.2.4.7	Listing of Urine Drug Test (Intent-to Treat)
Listing 16.2.4.8	Listing of Alpha Fetoprotein (Intent-to Treat)
Listing 16.2.5.1	Listing of Kit Numbers (Intent-to Treat)
Listing 16.2.5.2	Listing of Study Drug Administration-NGM282 (Intent-to Treat)
Listing 16.2.5.3	Listing of Study Drug Administration I-Rosuvastatin (Intent-to Treat)
Listing 16.2.5.4	Listing of Study Drug Administration II- Rosuvastatin (Intent-to Treat)
Listing 16.2.6.1	Listing of Liver Fat (%) (Intent-to Treat)
Listing 16.2.6.2	Listing of MRE and LiverMultiScan (Intent-to Treat)
Listing 16.2.7.1	Listing of Treatment Exposure and Compliance -NGM282 (Intent-to Treat)
Listing 16.2.7.2	Listing of Treatment Exposure and Compliance -Rosuvastatin (Intent-to Treat)
Listing 16.2.7.3	Listing of Adverse Events (Intent-to Treat)
Listing 16.2.7.4	Listing of Serious Adverse Events (Intent-to Treat)
Listing 16.2.8.1	Listing of Hematology (Intent-to Treat)
Listing 16.2.8.2	Listing of Chemistry (Intent-to Treat)
Listing 16.2.8.3	Listing of Urinalysis (Intent-to Treat)
Listing 16.2.8.4	Listing of Anti-Drug Antibodies and Neutralizing Antibodies (Intent-to Treat)
Listing 16.2.9.1	Listing of Vital Signs (Intent-to Treat)

Amendment Final V 2.0

Listing 16.2.9.2	Listing of ECG Values (Intent-to Treat)
Listing 16.2.9.3	Listing of ECG Results (Intent-to Treat)
Listing 16.2.9.4	Listing of Local Injection Site Symptom Assessment (Intent-to Treat)
Listing 16.2.9.5	Listing of Physical Examination (Intent-to Treat)
Listing 16.2.9.6	Listing of Pregnancy Tests (Intent-to Treat)
Listing 16.2.9.7	Listing of Prior Medications (Intent-to Treat)

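### SAP 5.2 and 5.3 define the Safety and Efficacy Populations by a dose of NGM282, which read literally removes the placebo arm; separately, antibody results could be given one descriptive by-arm table

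*SAP*

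**What the plan says.** **Populations.** SAP 5.1 states: "All randomized subjects will be included in the Intent-to-Treat (ITT) population". SAP 5.2 then limits the Safety Population to enrolled subjects with a full or partial dose of NGM282 and a post-dose safety evaluation. SAP 5.3 sets the same dosing condition for the Efficacy Population, which is the main population for efficacy and PD. Protocol 12.4.3 and 12.4.4 use study drug as the qualifying treatment. SAP 3.4 describes every subject in the cohort as treated with NGM282, then in the next paragraph gives the split as 50 NGM282 and 25 placebo.

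**Antibodies.** SAP 9.3 summarises hematology, biochemistry and urinalysis by treatment group and closes with "Anti-drug antibodies, neutralizing antibodies and urine microscopy evaluation will be listed only". The schedule in SAP Appendix A marks anti-drug antibodies (ADA) and neutralizing antibodies (NAb) at Day 1 and at Weeks 2, 4, 6, 8, 12, 18, 24 and 30, with no split by arm. Protocol 9.9.4 adds: "All NAb samples will be collected as scheduled, and analyzed only if necessary based on ADA results". The only readable antibody output is Listing 16.2.8.4, on the ITT population.

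**The concern.** All safety endpoints are to be summarised on the Safety Population, and 24-week safety and tolerability is a secondary objective. A rule that admits only NGM282 recipients leaves nothing to compare with: no placebo rate for adverse events, injection-site reactions or laboratory changes. The same rule in SAP 5.3 would leave the planned between-arm efficacy analyses with one arm. Protocol 12.4.5 and 12.4.6 build the Per Protocol and Liver Histology Populations as subsets of the Efficacy Population, so under that structure they would inherit the problem (SAP 5.4 and 5.5 are redacted).

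The antibody question is smaller. NGM282 is a recombinant protein injected daily for 24 weeks, and footnote b to protocol Table 1 links antibody formation in animals to drug accumulation. A listing contains no counts. Anyone wanting a rate must decide afterwards whether baseline positives count and which visits qualify, and the answer can depend on that choice.

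**Working it through.** **1. Qualifying treatment, side by side.**

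| Population | Protocol | SAP |
|---|---|---|
| Safety | 12.4.3: study drug | 5.2: NGM282 |
| Efficacy | 12.4.4: study drug | 5.3: NGM282 |
| ITT | 12.4.1: randomized | 5.1: randomized |

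Only the ITT definitions agree.

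**2. Size of the literal reading.** Planned enrolment is 50 + 25 = 75. Requiring a dose of NGM282 keeps at most 50 + 0 = 50 and drops 25/75 = 33.3%. The placebo column holds 0 of 25. A placebo subject given NGM282 by mistake would not refill it in the safety tables, because SAP 5.2 assigns by treatment actually received.

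**3. Does the rest of the SAP fit the literal reading?** It does not.
- SAP 8.2 names the Efficacy Population as the main population for secondary endpoints, and 8.2.1 compares treatment groups by ANCOVA.
- SAP 9.2 to 9.6 tabulate safety by treatment group.
- SAP 11 records no change from the protocol's planned analysis.

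Dropping placebo would contradict all three. With the loose wording of SAP 3.4, this points to a slip.

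**4. Antibody sampling.** The schedule gives 1 baseline visit plus 8 post-dose visits, 9 in all. Seven of the eight fall within the treatment period, and Week 30 is follow-up. Scheduled ADA samples: 75 × 9 = 675, of which 50 × 9 = 450 are on NGM282 and 25 × 9 = 225 on placebo. Post-dose: 75 × 8 = 600. The number of NAb assays cannot be predicted, since they depend on ADA results.

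**5. What is already defined.**
- Baseline (SAP 6.2.1): "the last available, valid, non-missing assessment reported on or before the start of first study drug administration".
- Treatment-emergent, for adverse events only (SAP 9.2): "TEAEs are defined as AEs that commence on or after the date of first study drug administration".
- Percentages (SAP 6.1): "with the denominator being the number of subjects in the relevant population, unless otherwise stated".

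What is missing from the readable text is a treatment-emergent rule for ADA and an incidence by arm. The default denominator would also count subjects never tested.

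**6. What a by-arm table could show.** The documents give no expected antibody rate, so the counts below are illustrative, with everyone evaluable. Exact (Clopper-Pearson) 95% limits are the 0.025 quantile of Beta(x, n−x+1) and the 0.975 quantile of Beta(x+1, n−x). For x = 0 the upper limit is 1 − 0.025^(1/n).

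| Ever positive after dosing | 95% CI |
|---|---|
| 0/50 | 0% to 7.1% |
| 5/50 | 3.3% to 21.8% |
| 10/50 | 10.0% to 33.7% |
| 0/25 | 0% to 13.7% |
| 2/25 | 1.0% to 26.0% |

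The placebo intervals are wide, so such a table is descriptive only.

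**The case against.** **On the populations:** a competent programmer would include placebo subjects without being told, because every planned table has treatment columns. That is fair as to intent. A reader might infer that the sponsor means to report safety without a control arm, but step 3 shows that the plan does not support this. What remains is that the written rule is wrong and differs from the protocol without being declared as a change.

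**On antibodies**, the other side is strong and most of it stands.
- Listing only is an explicit choice. No readable objective or endpoint asks for an antibody rate, and SAP 4.4 does not name one.
- Nothing is lost. The listing is on ITT, covers both arms and is sorted by treatment group (SAP 6.1). SAP 5.2 does not govern it, so the population wording removes no antibody result from the planned output.
- Possible clinical consequences, namely adverse events and injection-site reactions, are already tabulated by arm.
- The exploratory sections and the table index are redacted and could contain an antibody analysis. PK goes to a separate report, although SAP 2 does not mention immunogenicity there.

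A reader might infer from the animal footnote that antibody-driven accumulation in patients is going unexamined. The documents do not support that. Protocol 12.11.1 assesses accumulation through PK, and protocol 5.1.3 reports that the Phase 1 study in healthy volunteers saw none on repeat dosing. That study's summary gives no antibody rate, so it does not settle the question in NASH either.

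**Conclusion.** The population wording in SAP 5.2 and 5.3 is wrong as written. Taken literally it removes 25 of 75 planned subjects, the entire placebo arm, from every Safety- and Efficacy-population table. It is probably a slip, and on the evident intention no result changes. It should be corrected because population rules are meant to be applied as stated.

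The antibody point is a reporting gap of lower weight. It is not a conflict with the protocol and comes close to preference. It rests on the readable text only. A reader might go further and argue that assay background would distort a count taken from the listing. The documents give neither an assay error rate nor an antibody incidence, so no size can be put on that. Confidence that the visible plan contains no by-arm rate is good; confidence that none exists anywhere is only moderate, because of the redactions.

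**What to change.** **Correct.** In SAP 5.2 and 5.3, replace NGM282 as the qualifying treatment with study drug (NGM282 or placebo), and leave the rest of each definition alone. Naming both products matters because SAP 9.2 also counts rosuvastatin as study drug. Check that SAP 5.4 and 5.5 follow. Cost: one phrase in each section.

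**Consider.** Keep the antibody listing, and leave urine microscopy as listed only. Add to SAP 9.3 one descriptive table by arm and visit, on the corrected Safety Population, showing:
- number tested;
- ADA positive at baseline, as defined in SAP 6.2.1;
- treatment-emergent ADA, meaning negative at baseline and positive at a post-dose visit;
- NAb positive among those assayed;
- ever ADA positive after dosing, among subjects with at least one post-dose sample, with exact 95% CI.

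State each denominator in the table. Give no p-values and no comparisons of outcome by antibody status. Cost: one extra table, with no new samples or assays. If a redacted section already plans this, a cross-reference from SAP 9.3 is enough.
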